Considering that recruitment to the study was somewhat slower than expected in wave 1 and 2, and that the sample size recalculations showed that more housing units will be needed than initially estimated to reach power for detecting a 5 points difference, it was decided to re-dimension the study to detect a difference of 10 points. Wave 3 and 4 will recruit additional 42 housing units. The average attrition rate of the ELR and TAU arms combined after wave 2 was 33%. The same attrition rate in wave 3 and 4 would thus render in a total of $42 * 0.67 = 28$ new housing units. Monte Carlo simulations showed that adding 28 housing units to the presently included 17 units would give 80% power for detecting a group difference in ReQoL of 8.8 points. Code from the simulations is included as supplementary appendix.

Framework

The present study is a superiority trial, and all statistical tests will be of null hypotheses of the two arms being equal with respect to corresponding estimand.

Statistical interim analysis and stopping guidance

After the first wave, the internal pilot will be analyzed with respect to outcome variability, intra-class correlation drop out rate, adherence and required sample size for the full-scale study. While being an internal pilot, and hence its data will be included in the final analysis of full-scale study, the analysis at this stage will be non-comparative with respect to the study arms. Therefore, no adjustments of significance level in final analysis will be made.

Should there be unexpected problems revealed by the internal pilot, e.g. feasibility problems or that it is shown that an unrealistic large sample size will be required for the study to be conclusive, there is opportunity to stop the study. This decision will be made by the investigators, and if so, the result from the internal pilot along with the motivation for stopping the study will be published. No official stopping rule has been predefined.

Timing of final analysis

All outcomes, primary and secondary, will be analyzed collectively after the locking of the database, when data collection is finished. The study project also involves cost effectiveness analyses of ELR. These analyses may be performed and published at different occasion than the analyses described in the present SAP.

Timing of outcome assessments

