Measurements of ReQoL (primary outcome) RAS-DS (secondary outcome) will be conducted at baseline and at the 6-months follow-up, post-intervention. GAS, a secondary outcome, is only measurable for the intervention group at the 6-months follow-up.

Statistical principles

Confidence intervals and *P* values

A significance level of 5% will be employed in all hypothesis testing. The study includes one single primary outcome (ReQoL) and no adjustment to control for familywise type 1 error rate due to the multiple secondary outcomes will be performed. Precision of estimated parameters describing group differences will be assessed using 95% confidence intervals.

Adherence and Protocol deviations

Adherence to the intervention is defined as residents participating in at least 70% of the weekly sessions with occupational therapists. Further criteria for adherence are housing staffs completing the ELR education and housing managers asking the monthly follow-up questions at staff meetings. The adherence will be summarized and presented groupwise in the publication of study results. Violations of the study protocol will be included as an appendix to the published article of the final study.

Analysis populations

The primary analysis will use an intention-to-treat (ITT) approach and include all allocated participants with valid data, whether they did or did not receive the complete intervention.

A per-protocol population will be defined as participants following the adherence criteria listed under Adherence and Protocol deviations paragraph will also be made. The per-protocol population will be used for complementary, secondary analyses and presented in the study article.

Trial Population

Eligibility

Eligible participants are adults with severe psychiatric disability (SPD), living in sheltered or supported housing facility for people with SPD with access to occupational therapy.

Exclusion criteria are comorbidity of dementia or severe developmental disability, not being able to communicate in Swedish and currently being in acute psychosis, or acute suicidal risk.

Recruitment

In Figure 2, the planned information that will be reported in the flow chart of study participants is shown. Note that two more waves, wave 3 and 4, was added to reach sufficient power.

[figure not shown]

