Goal-attainment will be measured within the intervention group only, using the Goal Attainment Scaling (GAS)(4). The scale has 5 points representing different levels of mastery of the individual participant's goal, from -2 to +2, where a score of minus (-2 and -1) represents less change than expected, 0 represents the expected level of change/attainment, and plus (+1 and +2) represents achievement of more change than expected. GAS uses T-scores, where scores are rescaled so that T-scores have a mean of 50 and a standard deviation of 10. If all of the goals meet the expected level of achievement, the GAS T-score will be 50. A high T-score (50 or above) is reflective of expected or higher goal-attainment.

Only within-group changes will be analyzed. The GAS measurement is measured at the 6-months follow-up.

Analysis methods

Primary Outcome Measure (ReQoL):

A mixed effects models will be used. The dependent variable will be the ReQoL 6 months follow-up measurement. A random intercept effect for housing facilities will be included in the model. Fixed effects independent variables will be *group* (ELR or control) and *baseline ReQoL measurement*. The baseline ReQoL will be adjusted for, on both an individual participant level and on an aggregated cluster level using the average of the baseline measurement within the corresponding housing facility(5). The treatment effect is presented as the baseline-adjusted group effect at 6 months follow-up, along with its 95 % confidence interval.

Secondary Outcome Measure RAS-DS:

The same mixed effects models as for ReQoL is planned to be used. The dependent variable will be the RAS-DS 6 months follow-up measurement. A random intercept effect for housing facilities will be included in the model. Fixed effects independent variables will be *group* (ELR or control) and *baseline RAS-DS measurement*. The baseline RAS-DS will be adjusted for, on both an individual participant level and on an aggregated cluster level using the average of the baseline measurement within the corresponding housing facility. The treatment effect is presented as the baseline-adjusted group effect at 6 months follow-up, along with its 95 % confidence interval

Secondary Outcome Measure GAS:

GAS will be evaluated using paired t-test, comparing the pre- and post-intervention t-score.

Model assumptions

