Appendix – code for sample size recalculations

```
#Read libraries
library(tidyverse)
library(simr)
library(lmerTest)

#Fit mixed effects model, comparing REQOL post intervention between
#arms, adjusting for baseline REQOL.
mdl.interim <- lmer(REQOL_post ~ arm + REQOL_baseline + (1|unit),
data = df_interim)

#Extend sample size to 44 groups
mdl.interim_ext <- extend(mdl.interim, along = "unit",
n = 44)
)

#Set group difference to 8.8 points.

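### Is the per-protocol set left open because two of its three adherence criteria carry no threshold and TAU residents are not mentioned?

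*SAP*

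**What the plan says.** The SAP section Adherence and Protocol deviations opens with a numeric rule for residents: "Adherence to the intervention is defined as residents participating in at least 70% of the weekly sessions with occupational therapists". It then adds two facility-level conditions without numbers: "Further criteria for adherence are housing staffs completing the ELR education and housing managers asking the monthly follow-up questions at staff meetings".

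Analysis populations builds the set from that paragraph: "A per-protocol population will be defined as participants following the adherence criteria listed under Adherence and Protocol deviations paragraph". It also limits the set's role: "The per-protocol population will be used for complementary, secondary analyses and presented in the study article". Additional analyses says that every analysis is repeated on this set, that the results go to an appendix, and that a conclusion differing from intention-to-treat will be discussed. The repeated analyses include the ReQoL and RAS-DS models under Analysis methods, which compare ELR with control.

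The primary analysis is intention-to-treat and does not depend on any adherence criterion.

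**The concern.** A per-protocol set should be fixed before outcomes are seen, because its membership depends on what happened after randomisation. Here four points are unwritten: the share of a house's staff that must complete the education, the number of months in which the manager must ask the questions, whether a failing house takes its attending residents out, and how TAU residents enter. All three criteria describe delivery of ELR. A literal reader could therefore ask whether any TAU resident qualifies, and whether the group comparison could then be run at all.

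Two further features sharpen the worry. The SAP will comment on any disagreement between the two analyses, so the set bears on interpretation. Adherence was also among the pilot items: "the internal pilot will be analyzed with respect to outcome variability, intra-class correlation drop out rate, adherence and required sample size". The pilot houses stay in the final data, so a threshold chosen late might be chosen with some knowledge of its effect.

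**Working it through.** **1. What the text already settles**

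- *Attendance.* Fixed at 70% of sessions.
- *Staff education.* The condition is completion. The text offers no partial version, so the plain reading is that the staff have completed it.
- *Manager questions.* They are described as monthly, so the plain reading is every month.
- *House failure.* The two facility items are listed as further criteria, and the set is the participants who follow the criteria. The most direct reading is that all three must hold, so a resident of a failing house is out. The SAP does not spell this out.
- *TAU.* The criteria are introduced as adherence to the intervention, which TAU does not receive. The ELR-versus-control models are to be repeated on the set, which is impossible without TAU residents. The reading that fits both statements keeps all TAU residents.

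**2. How far the choice of rule could matter**

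The SAP gives no compliance data, so every input on compliance is an assumption. Taken from the SAP: 44 houses (Appendix), 2 residents per house, SD 10 and ICC 0.1 (Sample Size). Assumed: 22 houses per arm, 8 staff per house, 6 monthly occasions, no treatment effect, no baseline adjustment, and 70% of ELR residents meeting the attendance rule. This last 70% is a share of residents, not the SAP's 70% of sessions. ELR residents: 22 × 2 = 44; after attendance, 44 × 0.7 = 30.8.

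Rules compared: strict (all staff, 6 of 6 months), middle (at least 80% of staff, 5 of 6), lenient (half of staff, 3 of 6). Simulation with 10,000 runs per row and within-house correlation of compliance 0.3:

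| Compliance | ELR residents kept: strict / middle / lenient | SE strict | SE lenient | Ratio | Median difference, strict v lenient (points) |
|---|---|---|---|---|---|
| 80% | 6.5 / 13.1 / 24.4 | 4.48 | 2.62 | 1.71 | 2.3 |
| 90% | 14.6 / 21.0 / 28.2 | 3.19 | 2.50 | 1.28 | 1.2 |
| 95% | 21.4 / 25.8 / 29.7 | 2.74 | 2.46 | 1.11 | 0.8 |

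Without correlation, the counts are 7.0 / 22.2 / 30.8 at 90% compliance and 14.9 / 28.0 / 30.8 at 95%. Each rule alone rejects a true null in 4.6% to 5.2% of runs. Taking whichever of the three is significant gives 7.5% to 10.5% over all scenarios.

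**3. Check of the scale against the SAP's own figures**

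The original sample size reproduces: 63 residents per arm for 5 points at SD 10; 63 × 1.1 = 69.3; 69.3 / 2 = 34.65, so 35 houses per arm.

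The pilot superseded those inputs. With 44 houses they give SE = √(2 × 100 × 1.1 / 44) = 2.24. The SAP's later figures imply more:

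- 80% power at 8.8 points: 8.8 / (1.96 + 0.84) = 3.14, or 8.8 / 2.87 = 3.07 with t quantiles.
- 53% power at 5 points with 70 houses: 5 / (1.96 + 0.075) = 2.46; rescaled to 44 houses, 2.46 × √(70/44) = 3.10.

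Both give about 3.1, which is 3.1 / 2.24 = 1.38 times the SE used in the illustration. The lenient subset in the table (2.46 to 2.62) is thus more precise than the SAP's complete data would be, so the absolute SEs are too small. The ratios between rules and the false-positive rates do not depend on the SD.

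**4. What this shows**

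The spread comes from setting a near-literal rule against two that were constructed for the illustration. The inflated error rate needs an analyst who tries all three and reports the best. Neither is something the SAP plans.

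**The case for a change.** The strongest case for a change is that the gap lies in the SAP itself. The set is defined by reference to the SAP's own adherence paragraph, so a fuller protocol would not obviously close it. Reasonable analysts could differ on whether one untrained staff member disqualifies a house. If compliance is near 80%, the strict reading may leave about 7 ELR residents, which would tempt someone to relax it. A few lines of text would prevent that. This stands as a description of the wording.

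The pilot argument is weaker. With "adding 28 housing units to the presently included 17 units", the pilot share is 17 / 45 = 38%. The appendix code does fit an arm term, as its comment shows: "Fit mixed effects model, comparing REQOL post intervention between". However, the interim analysis section says the pilot analysis is non-comparative between arms, the code replaces the arm coefficient with 8.8, and no arm estimate is reported. Nothing in the SAP says that adherence and outcome were looked at together. Any tension between code and text is a separate matter and does not make the per-protocol definition wrong.

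The warning that comparing adherent ELR residents with all TAU residents invites selection bias is sound, but it holds whatever threshold is written. The SAP already commits to discussing differences from intention-to-treat.

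**Conclusion.** No change to the plan is needed. The four details are unwritten, but the plain reading fills them: staff complete the education, managers ask each month, all criteria must hold for an ELR resident, and all TAU residents stay in. Followed that way, the plan gives no wrong result. Writing it down would be harmless but would mostly restate that reading, and any looser threshold would remain the sponsor's choice.

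The stakes are small. The analysis is complementary and reported in an appendix; the primary estimate, sample size and type 1 error are untouched. The strict and lenient estimates differ by a median of 0.8 to 2.3 points. That range rests on assumed compliance of 80% to 95%, on assumed staffing and attendance, and on an SD and ICC that the SAP has since superseded. It measures distance from rules the SAP does not contain. The conclusion would differ if the per-protocol analysis carried a confirmatory claim, which it does not.

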Appendix – code for sample size recalculations

```
#Read libraries
library(tidyverse)
library(simr)
library(lmerTest)

#Fit mixed effects model, comparing REQOL post intervention between
#arms, adjusting for baseline REQOL.
mdl.interim <- lmer(REQOL_post ~ arm + REQOL_baseline + (1|unit),
data = df_interim)

#Extend sample size to 44 groups
mdl.interim_ext <- extend(mdl.interim, along = "unit",
n = 44)
)

#Set group difference to 8.8 points.
# This difference was identified by trial and error.
fixef(mdl.interim_ext)[["arm2"]] <- 8.8

# Set to Satterthwaite degrees of freedom in tests
simrOptions(lmerTestDdf = "Satterthwaite")
# Run simulations with 4000 repeats
pwr_recalc1 <- simr::powerSim(mdl.interim_ext,
nsim = 4000,
seed = TeachingDemos::char2seed("ELR"),
test = simr::fixed(xname = "arm2",
method = "t"),
progress = FALSE
)
```
